Exclusion criteria for Chronic pain cases (n=50) and Special Healthy Controls includes a) presence of active pelvic or abdominal malignancies (primary or metastatic), b) pregnancy, c) active genitourinary infection in the last four weeks, d) unable to read or comprehend the informed consent in English, e) unwilling to undergo study procedures (except internal PPT testing, visual sensory testing, hip or head PPT which may be waived in these groups), f) bilateral hand or knee pain, or g) absence of ovaries.

To summarize, Chronic Pain Cases and Special Healthy Controls may have absence of regular menses, hypertension, a history of epilepsy (in which case sensory testing will not be performed) or migraines with aura, and be unwilling/unable to abstain from hormonal contraception.

Phone Screen

All callers will complete a phone screen to assess eligibility before being scheduled for a screen

visit. Because of the drastically different inclusion/exclusion criteria, separate phone screens will be used for arm 1 (healthy control, dysmenorrhea, and PBS participants) than for arm 2 (special healthy control and chronic pain participants). At the end of the phone screen, all callers who complete an arm #1 or arm #2 phone screen will be asked if we have their permission to keep their phone screen information and contact them for future studies. Participants who indicate yes will be added to our recruitment registry study upon study closeout. Eligible callers will be scheduled for a screening visit.

Note we may attempt to match groups for age and demographics. Thus, in some cases, eligibility on the phone screen may vary based on the study's current need for individuals with certain demographics for each group. We may also require dysmenorrhea participants to endorse bladder symptoms on the phone screen in order for them to be eligible to come in for a screen visit.

Procedures Completed During Each Study Visit: During each testing session, participants will have their blood pressure and pulse taken, urine collected, and a urine pregnancy test (unless no uterus) completed.

C1.b Screening Visit: Informed consent will be obtained by a trained research assistant before any questionnaires or study procedures are completed.

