collected electronically using REDCap at home. If requested, paper versions can be provided instead and mailed in. For participants continuing to Phase 2, the year 1 annual medical history questionnaire will usually take place during their assessment #3 visit. All participants that complete phase 1 (Screen + Assessment #1), including phase 2 dropouts, will be asked to complete the annual follow-up questionnaire.

Group (Sample Size)	H (20)	D (20)	D+COS (95)	PBS (40)	P (50)	MSA
Bladder Pain at FU (VAS)	0	0	2.5	3.0	-	0.85
Pelvic Hyperalgesia (VAS)	0	0	3	3	-	0.84
Pelvic Hyperalgesia (Time)	0	0	2	2.5	-	0.83
Pelvic Pain Thresholds	0	.5	.5	2.3	-	0.81
Bodily Pain Thresholds	0	1.5	2	2	2.3	0.91
Conditioned Pain Modulation	0	1-2	1-2	4 _a	2-4 _b	0.94
Menstrual Pain History	0	3.7	5	6	-	0.81
Temporal Summation	0	0	.7	.8	-	-
Estradiol	0	1-3 _c	1-3 _c	1-3	-	0.84
Depression/Anxiety	0	.3	.4	2	2-4	0.82

Table X: Sample sizes and hypothesized results in Z-scores or range of Z-scores (relative to healthy) for subjects that are healthy (H), have dysmenorrhea (D), have cross organ sensitization (D+COS), PBS, or chronic pain (P). MSA indicates Kaiser's measure of sampling adequacy. Numbers in italics indicated minimum detectable hypothesized score with current sample size. Z-scores based on preliminary data, or others indicated by subscript (a: ⁹, b: ^{11,13}). Effects temporal summation in these populations are unknown, but effect sizes as large as 1.1 have been reported for fibromyalgia. Dashes (-) indicate unknown effect size.

C1.h Data Analysis/Sample Size Requirements: The primary outcomes under this hypothesis will be [1] bladder pain at FU, [2] pelvic hyperalgesia (VAS, time to return to baseline pain), reflecting peripheral dysfunction/sensitization, and [3] centrally mediated hyperalgesia (CPM, bodily pain thresholds).

Factor [1], Bladder pain at FU: Our preliminary data on healthy subjects and women with dysmenorrhea, in combination with other studies investigating migraine and PBS, suggests effect sizes between 1.4-5.6 (Cohen's d). As a control comparison, we expect that women with chronic pain will have levels of bladder and pelvic sensitivity comparable to healthy subjects. We will perform t-tests for each of these three pain variables using pairwise contrasts and appropriate Bonferroni corrections for six group comparisons.

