Factor [2], pelvic hyperalgesia: To confirm pelvic hyperalgesia (*but not necessarily pelvic PPT*) is higher in those with bladder pain, we will show bladder pain and pelvic hyperalgesia (both VAS and TIME) are higher in D+COS than healthy pain-free controls (H), dysmenorrhea only (D), and chronic pain patients (P). Similarly bladder pain, pelvic hyperalgesia and pelvic floor pain sensitivity (PPT) are anticipated to be greater in PBS than H, and D.

Factor [3], centrally mediated hyperalgesia: Greater central dysfunction manifest by impaired CPM and reduced bodily pain thresholds in vulnerable subjects will be shown by comparing D+COS, PBS, and P to D and H. We estimate 15 subjects per group will provide adequate power (g-power, a priori t-test, $\alpha=0.05$, $\beta=0.2$). To verify we have adequate phenotyping of CPM, we have included the positive control group with chronic pain (P). We assumed the

[figure not shown]
difference in CPM between healthy subjects and chronic pain patients in this protocol would have an effect size of 0.78 based on a meta-analysis (Lewis et al. 2012). Using a 2.6 allocation ratio, a priori power analysis ($\alpha=0.05$, $\beta=0.2$), suggests we need 20 healthy participants and as many as 50 chronic pain patients to detect a difference in the mean CPM. Additionally, the utilization of 50 chronic pain patients will allow us to use regression to identify up to 5 predicted factors associated CPM with correlation coefficients exceeding 0.3 even after correcting for multiple comparisons ($\alpha=0.05$, $\beta=0.2$) as suggested by an a priori random model power analysis. This will be readily captured as our global study design encompasses a larger sample size (Table X) to handle anticipated secondary analysis and projected needs for completion of Phase #2.

Additional confirmatory analysis: Special healthy control subjects (n=10), we will verify special healthy control subjects do not differ from original enrolled healthy control subjects (n=20) to ascertain chronic subjects (P) participating in the trial are not treated differently under blinded conditions.

For the secondary analysis of Phase #1, we will evaluate the D+COS (provoked bladder pain) phenotype while accounting for menstrual history (including historical OC exposure), hormonal factors, anxiety, and depression. To determine the relative contribution of these secondary variables on bladder pain, we will perform principal component analysis (PCA).

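### Phase 1 compares non-randomised groups by t-tests with no age covariate, and matching on age is optional, so an age gap between groups would enter the contrasts

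*Combined protocol and SAP*

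**What the plan says.** All references are to the combined protocol and SAP.

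- **Groups.** Sections B.1 and C1.a describe healthy controls (H), dysmenorrhea without bladder pain (D), dysmenorrhea with bladder pain (D+COS), PBS and chronic pain (P), aged 18-45. Membership follows from diagnosis and symptoms, not randomisation.
- **Balance by design.** The Phone Screen section says "we may attempt to match groups for age and demographics" and adds that "eligibility on the phone screen may vary based on the study's current need for individuals with certain demographics for each group". It gives no age bands, ratio, list of variables or balance check.
- **Primary test.** Section C1.h, under Factor [1], says: "We will perform t-tests for each of these three pain variables using pairwise contrasts and appropriate Bonferroni corrections for six group comparisons". No covariate is named. Under Factor [3], central dysfunction "will be shown by comparing D+COS, PBS, and P to D and H", again with no covariate and with a sample size computed for a t-test.
- **Secondary analysis.** Section C1.h evaluates the D+COS phenotype "while accounting for menstrual history (including historical OC exposure), hormonal factors, anxiety, and depression", using principal component analysis. Age is not on that list.
- **Phase 2, for comparison.** Covariate adjustment is planned there: E2 and P4 in section C2.h (Z1), and treatment deviations in section C2.j.

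**The concern.** The protocol treats age as something worth balancing, but neither the design nor the analysis secures that balance. Eligibility criteria differ between groups. P requires a documented disorder of more than six months that has needed at least two prescription treatments and/or surgery, and PBS requires medical records of chronic symptoms. The Phone Screen section itself describes the criteria of the two arms as very different. Groups that need an accumulated medical history may well be older than healthy volunteers.

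If age is related to pain thresholds or CPM, a t-test attributes the age difference to the pain phenotype. The contrast most exposed is H v P on CPM. Section C1.j uses the chronic pain group as a positive control to decide whether a null CPM result elsewhere can be believed. An age gap could create that difference or hide it.

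**Working it through.** **1. The plan's own figure.** Section C1.h sizes H v P on CPM with d = 0.78, allocation 2.6, alpha 0.05 and power 0.80, and states 20 healthy and up to 50 chronic pain women.
- Normal approximation, two-sided: n(H) = (1 + 1/2.6) × (1.960 + 0.842)² / 0.78² = 17.9, so 18 and 47.
- Exact noncentral t, two-sided: 19 and 49, power 0.81. At 20 and 50 the power is 0.83.
- One-sided: 15 and 39.

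The stated 20 and 50 therefore fit a two-sided t-test without a covariate, slightly rounded up.

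**2. Size of the bias.** The documents give neither group ages nor an age slope, so both are assumed: a gap of 5-10 years and a shift of 0.01-0.03 SD per year.
- Bias = years × slope: 5 × 0.01 = 0.05 SD to 10 × 0.03 = 0.30 SD, in either direction.
- Against the planned CPM effect: 0.05/0.78 = 6% to 0.30/0.78 = 38%.

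**3. False positive rate when age is the only difference.** The t statistic has noncentrality = bias × √(n1·n2/(n1+n2)).
- 20 v 50 (Table X and C1.h): √(1000/70) = 3.78, so noncentrality 0.19-1.13 on 68 df.
- 40 v 43 (healthy and chronic pain women expected to complete Phase 1, section B.1): √(1720/83) = 4.55, so 0.23-1.37 on 81 df.

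| Two-sided level | No bias | 20 v 50 | 40 v 43 |
|---|---|---|---|
| 0.05/6 = 0.0083 | 0.8% | 0.9-6.3% | 1.0-9.7% |
| 0.05, uncorrected | 5% | 5.4-20% | 5.6-27% |

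The Bonferroni sentence sits under Factor [1]. I read it as covering the Phase 1 primary contrasts generally, although the CPM sample size uses 0.05. Bonferroni lowers the rate but does not remove the bias.

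**4. The bias against the expected effects.**
- Bladder pain, d 1.4-5.6: at most 0.30/1.4 = 21%, and 5% at the upper end.
- Pelvic hyperalgesia, 2-3 in Table X: at most 15%.
- Bodily thresholds, 1.5-2.3 in Table X: at most 20%.
- CPM, H v P: at most 38% of the 0.78 used for sample size. Table X projects 2-4 for P, against which it is at most 15%.
- Smaller Table X values: pelvic thresholds in D and D+COS (0.5), at most 60%; temporal summation (0.7-0.8), at most 43% and 38%. Neither is in the C1.h list of primary outcomes.

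**5. Cost of adjusting, 20 v 50, d = 0.78, two-sided 0.05.** Let r be the age-outcome correlation (assumed 0.1-0.3) and g the age gap in SD of age. Effective d = 0.78/√(1−r²) × √(1−R²), with R² = p(1−p)g²/(1+p(1−p)g²), p = 20/70 and 67 df. For g = 1, R² = 0.204/1.204 = 0.169.

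| Age gap | Power, age-adjusted |
|---|---|
| none | 0.83-0.86 |
| 0.5 SD | 0.81-0.84 |
| 1 SD | 0.76-0.79 |

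Unadjusted power is 0.83. A gap above 1 SD would cost more.

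**The case against.** The strongest reply is that the size is assumed throughout. If the ages balance, or age is unrelated to the outcome, there is no bias. At the low end of the range the error rate is essentially nominal. Most projected effects are several times the largest assumed bias. All of that stands, and it limits the point to CPM and the smaller effects.

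Four stronger readings are tempting, and the documents do not support them.

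- *That all five groups come by different routes.* D and D+COS enter under the same dysmenorrhea criteria and are separated by bladder pain at assessment visit 1 (sections C1.a and C1.b). An age gap between them is possible but does not follow from recruitment. Section C1.a does not tie any advertising channel to healthy controls.
- *That matching would invalidate the t-test.* The matching described is at group level, through phone-screen eligibility, not matched pairs. An unpaired t-test after such balancing is not biased by the balanced factor and is, if anything, slightly conservative.
- *That Phase 1 rests entirely on these contrasts.* It also plans principal component analysis, a regression for CPM in chronic pain, and cluster analysis. None of them lists age or gives an age-adjusted group contrast.
- *That false positive rates of 20% or 27% apply.* Those belong to an uncorrected 0.05 and the top of both assumed ranges.

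One further objection has substance. Under the section A hypothesis that repeated menstrual pain raises vulnerability, age partly stands in for cumulative exposure. The age-adjusted contrast then answers a somewhat different question. That is a reason to show both estimates, not to omit the adjusted one.

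**Conclusion.** The gap is real and modest. Phase 1 contrasts of non-randomised groups have no age covariate, matching is discretionary, and the secondary analysis does not fill the gap. The contrasts most open to it are PBS or P against H or D, where eligibility criteria differ.

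The range of 0.05-0.30 SD rests wholly on the assumed age gap and slope, and its direction is unknown. It would not overturn the expected bladder pain differences. It could matter for the H v P CPM contrast, on which the reading of a negative CPM finding depends, and for effects of 0.5-0.8. This is a cheap improvement to the plan; the documents do not show that the Phase 1 results would be wrong.

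**What to change.** In section C1.h, replace each Phase 1 t-test by the same contrast from a linear model with group and age, with age prespecified. Add any demographic variable that was actually used to balance recruitment, and name it; the documents name none beyond age. Keep the Bonferroni correction for six comparisons. Report the unadjusted difference beside the adjusted one, with age by group. Leave anxiety, depression, hormones and menstrual history to the secondary analysis, since some may lie on the causal path.

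Age is already needed for eligibility, so no new data are required. The cost is a change of wording, one or a few degrees of freedom, and some power if the groups differ strongly in age: from 0.83 to 0.76-0.79 at 20 v 50 with a 1 SD gap, which is when the unadjusted test is least reliable.

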To evaluate bodily pain pressure thresholds, we will assess three external measurement sites corresponding to American College of Rheumatology fibromyalgia tender point sites: the right trapezius, the right medial knee fat pad, and the right greater trochanter.⁴⁵ One additional site will be a sham tender point, the middle of the forehead. A digital algometer (described above) will be used to conduct the external site measurements using a ramp rate of 0.5 kg/cm²/s. Trials of the shoulder, hip, and knee may be terminated by examiner at 7.0 kg/cm² and trials of the forehead may be terminated at 4.0 kg/cm² in the case that the subject does not reach pressure pain threshold before then. Subjects will report level of pain at the time they pressed the button on a NRS 0-10 scale immediately after testing each individual site. After a two-minute break, the sites will be retested again.

Next, we will use the vaginal algometer (described above). The four pelvic sites will be accessed by intravaginal exam, with all measurements conducted using the right index finger

(Diagram 3) and a ramp rate of 0.5 kg/cm²/s. Internal trials may be terminated by examiner at 3.0 kg/cm². A trained clinician will perform all pressure-pain tests. Subjects will report the pain at the time they pressed the button on a NRS scale immediately after testing each individual site. After a two-minute break, the sites will be retested again. In order to compare within-subject results from the three assessment visits and in order to standardize timing of post-testing time scores (collected every 5 minutes as described below), the order of testing sites will not be counterbalanced.

Subjects will be allowed to rest for another 5 minutes, and subject will be queried on the level of NRS pain at each site again (shoulder, hip, knee, forehead, global vagina). Subjects will be queried every 5 minutes until pain returns to baseline levels or up to 30 minutes (the time of resolution in minutes will also be recorded).

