Conditioned Pain Modulation (CPM) : CPM testing involves repeating pressure pain threshold testing in the presence of a heterotopic stimulus (in this case cold water). The testing stimulus will be a mechanical pressure on the left medial knee fat pad. As in the first task, pressure will be applied (0.5 kg/cm²/s ramp) until the participant achieves pressure pain threshold. Baseline pressure pain thresholds of the testing stimulus on the left knee and left shoulder will be determined. After waiting approximately 2 minutes, the conditioning stimulus will be applied by instructing the subject to insert their right hand up to their wrist into a bucket of water maintained between 0-6° C. After 10 s of immersion, subjects will be asked to rate their level of hand pain on a NRS 0-10 scale. After 20s of immersion, the pressure pain threshold will be re-applied using a 0.5 kg/cm²/s ramp rate at the knee and the participant will be asked to rate their knee pain at the time they reached threshold (i.e. pressed the button) on a NRS 0-10 scale. After testing (~20s of immersion), subjects will immediately remove their hand and the pressure pain threshold will be determined at the shoulder. After waiting 5- and 10-minutes after water immersion, the testing stimuli will be re-applied. This paradigm combines a method for measuring CPM⁴⁶ and methods for accurately measuring participation of descending inhibition.⁴⁷ CPM will be measured by the standardized differences in pain threshold, EMG activity and autonomic responses before and after heterotopic stimulation. This strategy will provide the most reliable measurement of descending inhibition.^{47,48}

Temporal Summation (TS): Participants will be instrumented to undergo tests of spinal pain modulation. Temporal summation will be tested using an algometer on the right medial knee fat pad. We will repeatedly apply an amount of pressure (0.5 kg/cm²/s ramp rate; ITI = 5-15 seconds) equal to the average of the participant's two pressure pain thresholds assessed during the first task. After each press, the participant will be asked to rate their pain on an NRS 0-10 scale. The pressure will be applied ten times or until the participant rates their pain as a 6, whichever comes first.

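### If the 7.0 kg/cm² stopping limit applies in CPM testing, healthy women near it cannot show their full rise, and the planned t-tests can bias CPM contrasts with the healthy group toward zero

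*Combined protocol and SAP*

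**What the plan says.** **First pressure task** (C1.e, Pressure Pain Threshold Test). "Trials of the shoulder, hip, and knee may be terminated by examiner at 7.0 kg/cm²". This covers a participant who has shown no threshold at that pressure. The forehead has a like provision with a limit of 4.0 kg/cm². For the vaginal sites, "Internal trials may be terminated by examiner at 3.0 kg/cm²". Stopping is permitted, not required.

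**CPM task** (C1.e, Conditioned Pain Modulation). The test sites are the left knee and left shoulder. "As in the first task, pressure will be applied (0.5 kg/cm²/s ramp) until the participant achieves pressure pain threshold". No limit is restated. The outcome is a before-and-after comparison: "CPM will be measured by the standardized differences in pain threshold, EMG activity and autonomic responses before and after heterotopic stimulation".

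**Analysis.** C1.h makes CPM and bodily pain thresholds the third Phase 1 primary outcome. The stated Phase 1 method is "We will perform t-tests for each of these three pain variables using pairwise contrasts and appropriate Bonferroni corrections for six group comparisons". For the central factor, "Greater central dysfunction manifest by impaired CPM and reduced bodily pain thresholds in vulnerable subjects will be shown by comparing D+COS, PBS, and P" with D and H. In Phase 2, analysis Z2 (C2.h) uses repeated measures ANOVA for thresholds and CPM.

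**Data handling.** Section D says that threshold values are saved automatically and that values beyond two standard deviations are reviewed. No section says what is recorded for a trial stopped without a threshold, whether it is flagged, or how it is analysed.

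**The concern.** A trial stopped at 7.0 kg/cm² without a threshold shows only that the threshold is at least 7.0. CPM is a within-woman difference in threshold, so a cap limits the rise that can be recorded. A woman who starts at 6 can show a rise of at most 1, and a woman capped at baseline can show none.

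The cap would not fall evenly. Table X puts the bodily-threshold gap from healthy at 1.5 SD (D), 2 (D+COS), 2 (PBS) and 2.3 (P), and C1.h expects reduced thresholds in the vulnerable groups. Healthy women are therefore the ones most often near the limit, and they are also the ones expected to show the strongest inhibition. The healthy rise would be cut while the patients' rise is recorded nearly in full.

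The contrast most at stake is healthy versus chronic pain. C1.j uses the chronic pain group as the positive control that is to show the paradigm could detect a CPM deficit, and so to validate a negative result. A ceiling could make a working paradigm look as if it had failed.

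**Working it through.** **1. The plan's own figure.** C1.h gives an effect size of 0.78, an allocation ratio of 2.6, alpha 0.05 and power 80%, and states 20 healthy and up to 50 chronic pain participants. The exact two-sided t calculation needs 18.4, so 19, healthy women, and 19 × 2.6 = 49.4, so 50 patients. This agrees with the plan. At 20 v 50 the noncentrality is 0.78 × √(20 × 50 / 70) = 2.95 on 68 degrees of freedom, and power is 82.8%.

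**2. Inputs for the ceiling check.**
- From the documents: limit 7.0 kg/cm²; 20 healthy (H) v 50 chronic pain (P); true CPM difference 0.78 SD of change.
- Assumed, because the documents do not give them: normal thresholds; baseline SD 1.5; change SD 1.0, independent of baseline; mean rise 1.0 in H and 1.0 − 0.78 = 0.22 in P; P baseline 1.5 SD (2.25 kg/cm²) below H, which is milder than Table X's 2.3; limit applied to every CPM trial; healthy mean 3, 4, 5 or 6.

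**3. Formula.** Recorded CPM = min(B + Δ, 7.0) − min(B, 7.0), with B the baseline and Δ the true rise. For a normal variable with mean μ and SD σ, capping at 7.0 lowers the mean by L(μ, σ) = (μ − 7)Φ(z) + σφ(z), where z = (μ − 7)/σ. The conditioned threshold has SD √(1.5² + 1.0²) = 1.803.

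**4. Worked case, healthy mean 5.**
- H: L(6, 1.803) = 0.327 and L(5, 1.5) = 0.064. Recorded rise = 1.0 − 0.327 + 0.064 = 0.736 (rounded from unrounded terms).
- P: L(2.97, 1.803) = 0.008 and L(2.75, 1.5) = 0.001. Recorded rise = 0.22 − 0.008 + 0.001 = 0.213.
- Difference = 0.736 − 0.213 = 0.523, and 1 − 0.523/0.78 = 33% lost.

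**5. All four means.** Power is from 20,000 simulated trials per row, Welch t-test at 0.05. Without a cap it is about 82%.

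| Healthy mean (kg/cm²) | H at limit in at least one trial | H at limit at baseline | Recorded difference | Fall | Power |
|---|---|---|---|---|---|
| 3 | 5% | 0.4% | 0.746 | 4% | 80% |
| 4 | 14% | 2% | 0.673 | 14% | 74% |
| 5 | 30% | 9% | 0.523 | 33% | 56–57% |
| 6 | 51% | 25% | 0.314 | 60% | 28% |

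**6. Sensitivity.** If P has the same baseline as H, power at means 4, 5 and 6 is 79%, 72% and 59%. A second set-up fixes the share of healthy women capped at baseline, puts P 2.3 SD lower and sets the change SD at half the baseline SD. Shares of 5%, 10% and 20% give an observed effect of 0.69, 0.62 and 0.52, and power of 73%, 64% and 48%.

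**7. Where the effect is small** (assumptions of step 2, means 4, 5 and 6).
- D v D+COS, with a true 0.78 difference, loses about 1%, 3% and 9%.
- A full rise of 1.0 in D+COS women, 2 SD below healthy, is under-recorded by 0.2% to 3.5%.
- The bodily-threshold difference shrinks by at most about 10%. In the second set-up, with 20% of healthy women at the limit, power for gaps of 1.5 to 2.3 SD stays above 99%.

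**8. Does a censored analysis help?** A joint normal model of baseline and conditioned thresholds, right-censored at the limit, was run in the second set-up with 5% to 30% of healthy women capped at baseline (250 trials per setting). It gave a median estimate of 0.74 to 0.82 against the true 0.78, and power of 72–86%, against 10–73% for the t-test. Monte Carlo error is 2 to 3 points, and the likelihood-ratio test may be slightly liberal with 20 healthy women.

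**The case against.** The strongest reply is that the limit is not written for CPM. It belongs to the first task, and the CPM text says pressure goes on until threshold. That stands: the reference back to the first task only implies the limit. The bias is therefore conditional, and reconciling the two sections comes first.

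The second reply is that the size rests on invented distributions. This also stands. At a healthy mean of 3 the loss is trivial. Table X also hypothesises larger CPM gaps for chronic pain (2 to 4) than the 0.78 used here; 0.78 is used because the plan's sample size for this contrast rests on it.

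Third, silence is not proof of mishandling. C1.e allows a measurement that was not obtained to be repeated, and it defers to published protocols and a supplement that are not in the document. But a repeat in a woman whose threshold exceeds 7.0 ends at the same limit, and the analysis sections still lack a rule. CPM also draws on EMG and autonomic responses, which the limit does not cap; their weight is not stated.

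A reader might infer that all CPM contrasts shrink, that Phase 2 gains are hidden, or that the forehead and vaginal limits add to the problem. The documents do not support this. The symptomatic groups all start well below healthy, so contrasts among them, including D+COS or PBS v D, and the D+COS changes in Phase 2 are nearly untouched (step 7). The forehead and vagina are not CPM sites.

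**Conclusion.** The point holds in a conditional form. What is certain is that C1.e leaves unclear whether the 7.0 kg/cm² limit applies in CPM, and that no rule covers a trial stopped without a threshold. If the limit applies, the direction follows from the plan's own expectations: CPM contrasts with the healthy group, including the positive control, can be biased toward zero. The size is unknown. Over assumed healthy means of 3 to 6 kg/cm² the healthy v chronic pain difference falls by about 4% to 60%, and power falls from about 82% to between 80% and 28%, given the normality, SD and baseline-gap assumptions in step 2. It would be too strong to say that the CPM results are biased, since neither the use of the limit in CPM nor the share of healthy women near it is documented. The change should be made because it is cheap and protects a primary outcome and its positive control.

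**What to change.** Leave the test procedures as they are and amend the analysis text.

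1. Reconcile the pressure-threshold and CPM sections of C1.e, so that it is explicit whether the limit applies in CPM trials.
2. Flag every trial stopped without a threshold as right-censored at the pressure reached, and report the share by group, site and time point.
3. For CPM contrasts with the healthy group, prespecify a censored-normal analysis, either as the main analysis or as a sensitivity analysis beside the t-test. Model baseline and conditioned thresholds jointly, so that women capped at baseline stay in. Excluding them could remove about a quarter of the healthy group (5 of 20) at an assumed mean of 6.
4. Do not recode thresholds actually reached above 7.0 as censored, unless stopping was applied inconsistently. Otherwise real data are discarded and a ceiling is created.

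The cost is a few sentences, one data flag and slightly more analysis work. Section D does not say what is saved for a stopped trial, so the flag may have to be recorded at testing or taken from the session notes. The model assumes normality, which 20 healthy women can test only weakly. If few trials are stopped, its results should be close to those of the t-test and little is lost.
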